8.4.1 Patients with Single DEB-TACE Procedure

The following laboratory testing will be performed 1, 7±4, 30±7, 90±14, 180±14, 270±14, and 360±14 days following DEB-TACE: CBC, coagulation panel, BUN, creatinine, and liver function tests. Serum alpha-fetoprotein testing will start approximately 30 days following last planned DEB-TACE procedure. Any abnormal lab values will be followed up as clinically indicated. Laboratory tests may be performed at UCSF or at a local lab.

Seven ±4 days following DEB-TACE patients will have clinic follow up in Interventional Radiology for toxicity monitoring including reviewing the laboratory results above. Any expected or unexpected AEs will be discussed with the study PI or a designated co-investigator. Further testing and/or treatment will be coordinated by the study PI or a designated co-investigator if clinically appropriate (see section 7).

Cardiac function assessment monitoring using echocardiogram will be obtained approximately 30 days following the DEB-TACE procedure.

Patients will be seen in clinic approximately one month after the DEB-TACE procedure. During this visit, interim medical history will be obtained, and a physical examination will be performed. This will include (but will not be limited to) cardiopulmonary evaluation and an abdominal exam. Subsequently, patients will be followed in clinic at approximately 3 month intervals until 360 days following DEB-TACE.

Approximately one month after DEB-TACE procedure, patients will undergo repeat cross-sectional imaging with multi-phase contrast-enhanced CT or MRI of the abdomen. Subsequent imaging will be performed at approximately 3 month-intervals until 360 days following DEB-TACE. Standard clinical practices will be adhered to during the follow-up period.

Response to treatment will be assessed according to the RECIST version 1.1 and mRECIST criteria (see section 9.2).

Patients will be removed from study and follow-up assessments will stop prior to 360 days following DEB-TACE if a patient:

- a) requires > 4 DEB-TACE procedures
- b) requires another anti-cancer treatment modality such as ablation, surgery, or conventional TACE
- c) receives a liver transplant
- d) develops untreatable intrahepatic or extrahepatic disease progression
- e) experiences unacceptable toxicity (see section 10.0). All serious adverse events will be followed until the SAE has been resolved.

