12.3 Analysis Plan

Demographics and Baseline Characteristics

Demographic and baseline laboratory results will be summarized using descriptive statistics.

Safety Analysis

Patients will be monitored for development of recognized complications of DEB-TACE including liver dysfunction, renal dysfunction, ascites, hepatic encephalopathy, hepatorenal syndrome, biliary injury (stricture or leak), cholangitis, cholecystitis, hepatic abscess, abdominal pain, nausea, vomiting, fatigue, and fever. Adverse events will be graded according to NCI CTCAE version 4.03. Prevalence of adverse events will be summarized using descriptive statistics.

Efficacy Analyses

Analyses will be performed using the intent to treat population with exceptions as defined below, which require patient replacement.

Primary efficacy analysis

Primary efficacy will be evaluated as 1-month radiographic response after last DEB-TACE procedure in treated HCC lesions according to 1) RECIST version 1.1 and 2) mRECIST. Patients who do not have any post-baseline tumor assessments will be counted as non-responders. Point estimates of response rate and confidence intervals will be provided.

Secondary efficacy analyses

1. Overall radiographic response by 1) RECIST 1.1 and 2) mRECIST 6 months after the date of the first planned DEB-TACE procedure. This analysis will take into account all measurable hepatic HCC lesions present on cross-sectional imaging 6 months after the date of the first planned DEB-TACE procedure.
2. Time to untreatable progression (TTUP). TTUP is defined as time to disease progression untreatable by liver-directed percutaneous or surgical methods as assessed by treating investigator(s). Patient follow-up up to 1 year after last DEB-TACE will be allowed for this outcome variable.
3. Time to progression (TTP). TTP is defined as the time interval between date of first DEB-TACE procedure and date of imaging documenting development of intra- or extrahepatic disease progression by 1) RECIST 1.1 and 2) mRECIST. Patient follow-up up to 1 year after last DEB-TACE will be allowed for this outcome variable.

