10. Biochemical response defined as $\geq 50\%$ decrease in alpha-fetoprotein level measured 1 month and 4 months after DEB-TACE.
11. Histopathologic response defined as percentage of tumor necrosis at liver explant histopathology. This will only be explored in the subgroup of patients who undergo a liver transplant. Per UCSF clinical standard, tumor necrosis for HCC lesions is reported as 100%, >90%, 60-90%, 30-59%, and < 30%.

Intention To Treat Exceptions (Patient replacement)

1. Patients who proceed to liver transplant or develop hepatic decompensation between the time of enrollment and the first DEB-TACE treatment will be replaced.
2. Patients who proceed to liver transplant prior to completion of the 1 month safety window after first DEB-TACE will be replaced unless the transplant occurred due to hepatic decompensation or other toxicity attributed as at least possibly-related to protocol therapy, in which case the hepatic decompensation or other toxicity will be deemed a serious adverse event and the patient will be included in safety analysis (see Section 14.1.3).

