14.2 Adverse Event Grading

All AEs will be graded according to the NCI Common Terminology Criteria for Adverse Events (CTCAE) version 4.03.

Severity of AEs will be graded using the following general definitions of the CTCAE v4.03 :

- Grade 1 – Mild (no limitations)
- Grade 2 – Moderate (some limitations)
- Grade 3 – Severe (requires medical attention; usual activities stop)
- Grade 4 – Life-threatening/disabling (requires immediate medical help)
- Grade 5 - Death

Causality of AEs will be graded by the treating investigator with review by the Study Chair as follows:

- Unrelated
- Unlikely related
- Possibly related
- Probably related

- Definitely related

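### Treated patients transplanted within 1 month are replaced, and the plan places them in the safety analysis only if the transplant is attributed to treatment toxicity

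*Combined protocol and SAP*

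**What the plan says.** Section 12.3 sets the efficacy population as follows: "Analyses will be performed using the intent to treat population with exceptions as defined below, which require patient replacement". Two exceptions are listed. Item 1 concerns patients who were never treated and is not at issue here. Item 2 concerns patients who have already been treated: "Patients who proceed to liver transplant prior to completion of the 1 month safety window after first DEB-TACE will be replaced". It then carves out one case, a transplant brought on by decompensation or another toxicity judged at least possibly related to treatment. For that case alone the text adds that the event "will be deemed a serious adverse event and the patient will be included in safety analysis".

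Other provisions bear on the point:

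- Section 12.3, primary efficacy: "Patients who do not have any post-baseline tumor assessments will be counted as non-responders".
- Section 12.3, Safety Analysis: adverse events are summarised descriptively. No safety population is defined.
- Section 14.2: "Causality of AEs will be graded by the treating investigator with review by the Study Chair".
- Section 13.5.3: all grade 3-5 events are entered in the database whatever their attribution.
- Section 9.1: the final safety analysis is timed from the treatment of all 51 patients.
- Section 8.4.1, single-session patients: "Approximately one month after DEB-TACE procedure, patients will undergo repeat cross-sectional imaging". The Abstract gives the window as 30±7 days.

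**The concern.** Safety is a primary objective, and its natural denominator is everyone exposed. Item 2 acts after exposure. For a treated patient transplanted early, the only stated route into the safety analysis is a judgement that treatment toxicity caused the transplant. A patient may have a grade 3 or 4 liver or renal event in week 2 and receive an organ in week 4 for reasons judged unrelated. The plan gives that patient no place in the safety analysis. Such removals can only lower the reported toxicity rate if the patients removed carry events more often than their replacements do, and that is plausible when events before the transplant are already known.

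The efficacy side has a related problem. Most patients transplanted inside the first month will not have had their response scan. The primary efficacy rule would count them as non-responders, but item 2 takes them out of the denominator, so the response rate rises.

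**Working it through.** **1. Which treated, transplanted patients have a stated place in each analysis?**

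| Treated patient | Replaced? | Safety analysis | Response analysis |
|---|---|---|---|
| Transplant within 1 month, attributed to toxicity | No | Stated: included | Non-responder if no scan |
| Transplant within 1 month, other reason, no scan | Yes | Not stated | Removed, though the general rule says non-responder |
| Transplant within 1 month, other reason, scanned on days 23-29 | Yes | Not stated | Removed with a result in hand |
| Multi-session, transplant at day 45, no scan | No | Not excluded | Non-responder |

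Once one treated patient has been replaced, more than 51 people have been exposed. Section 9.1 still refers to 51.

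**2. How many early transplants?** Section 1.1 gives a typical wait of 1.5-2 years. Reading that as an exponential median m (assumption), the one-month probability is 1 − 2^(−1/m).

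- m = 18 months: 3.78%; × 51 = 1.93.
- m = 24 months: 2.85%; × 51 = 1.45.
- If only half of the 51 are listed (25.5): 0.96 and 0.73.
- If the wait is instead read as a mean, 1 − exp(−1/m) gives 5.40% and 4.08%, or 2.8 and 2.1 of 51.

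**3. How many of these carry a countable toxicity?** Assume independence and apply the historical conventional-TACE rates in section 10.1.1.

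- Persistent grade 4 liver toxicity, 12%: 0.12 × 1.45 = 0.17; 0.12 × 1.93 = 0.23.
- Persistent grade 4 renal toxicity, 1.2%: 0.012 × 1.45 and 0.012 × 1.93, each about 0.02.

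The descriptive safety summary also covers events that resolve. In the 37 DEB-TACE patients of section 1.2, up to 10 (9 + 1, or 27%) had reversible grade 3 or 4 bilirubin: 0.27 × 1.45 = 0.39; 0.27 × 1.93 = 0.52. Either way, fewer than one such patient is expected.

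**4. What does one such patient do to the toxicity rate?** Take 6 events in 51 (11.8%) after one affected patient has been replaced by an unaffected one. Keeping the replaced patient gives 7/52 = 13.5%, a difference of 1.7 points.

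**5. What happens to the response rate?** At the smallest successful result, 15/51 = 29.4%. Adding back replaced patients as non-responders gives 15/52 = 28.8% for one and 15/53 = 28.3% for two.

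**6. How often is a response result already known?** This needs a single session, a scan on days 23-29, and then a transplant before the month ends. If all 51 were listed, single-session and scanned on day 23, seven days at the hazard in step 2 gives at most 0.34-0.45 patients.

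**7. Design check.** An exact calculation with boundaries 4/17 and 14/51 reproduces the plan: early stop 75.8% at a 20% response rate and 12.6% at 40% (stated 76% and 13%), type I error 4.87%, power 85.4%. If a share t of the 51 were transplanted early and counted as non-responders, so that p becomes p(1 − t), power at 40% falls to 82.4% (t = 3%) or 81.3% (t = 4%). Type I error falls to 3.9% or 3.6%.

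**The case against.** **The exceptions are for efficacy only.** They are invoked under the efficacy heading, and the Safety Analysis paragraph contains no exclusion. Part of this stands: exclusion from safety is inferred from what item 2 leaves unsaid and is not expressly stated. But item 2 itself says who enters the safety analysis, and no all-treated set is defined elsewhere to override it.

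**Nothing is hidden.** Grade 3-5 events are recorded regardless of attribution, reviewed monthly by the site committee, and summarised quarterly to the monitoring committee. This stands. Events can leave the analysis, but they do not leave the record or the oversight process.

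**The attribution safeguard is reasonable.** The threshold is low (at least possibly related), and the Study Chair reviews the grading. This reduces the risk. It does not make attribution a suitable condition for entry to a safety denominator.

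**A reader might infer that replacement takes patients out of the safety stopping counts.** The documents do not support this. Section 10.1.2 does not mention replacement, and Table 4 is indexed by patients enrolled, which a replaced patient was. The liver and renal rules also turn on failure to improve within 1 month, so the status of a patient transplanted before then is unsettled with or without replacement. The renal threshold is only 2 patients, however, so the silence is worth closing.

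**A reader might also infer that known responses are routinely deleted.** Step 6 shows this is a corner case. The usual effect is to remove would-be non-responders.

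**The day-45 contrast is not a bias.** Counting an unscanned multi-session patient as a non-responder is conservative and pre-specified. This stands; the contrast shows only that the two rules treat similar patients differently.

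**Conclusion.** The concern holds in a limited form. As written, item 2 makes the safety denominator for some treated patients depend on a causal judgement made after exposure, with a possible downward bias in the toxicity rate. It also overrides the non-responder rule for some treated patients, which nudges the response rate upward.

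The size is modest. About 1.5-1.9 of 51 patients would be transplanted early, or 0.7-1.0 if half are listed, and fewer than one of those is expected to carry a severe event. These figures assume a constant transplant hazard, a typical wait read as a median, and independence between toxicity and early transplant. The documents give none of these; with the wait read as a mean, early transplants rise to 2.1-2.8. Section 4.2 admits patients who are only being screened for transplant, so full listing is an upper case.

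No stated sample-size, power or early-stopping figure is wrong on this account. The point deserves correction because the affected analysis is primary and the correction is cheap.

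**What to change.** Amend section 12.3 as follows:

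1. Define the safety population as every patient who receives any DEB-TACE, with events counted up to transplant whatever the reason for transplant.
2. State that replacement does not remove a patient from the counts used for the section 10.1.2 safety rules.
3. State that a patient with a post-baseline scan is counted on that scan and is not replaced.
4. Keep replacement of treated patients within the current 1-month window. Extending it to the primary scan would be unsound. That scan may fall up to 6 months after the first procedure, when 1 − 2^(−6/24) = 16% to 1 − 2^(−6/18) = 21% of listed patients could have been transplanted on the same hazard. The extension would also remove patients now counted as non-responders.
5. Report the number of replaced patients with reasons, and add a sensitivity analysis that counts replaced treated patients as non-responders.

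The cost is a few sentences, and the reported toxicity rate may be slightly less favourable. Unscanned patients transplanted early for reasons unrelated to toxicity stay replaceable for efficacy, so the primary test avoids the power loss shown in step 7.

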13.0 ETHICAL AND REGULATORY CONSIDERATIONS

13.1 Pre-study Documentation

This study will be conducted in accordance with the ethical principles that have their origin in the Declaration of Helsinki as stated in 21 CFR §312.120(c)(4); consistent with GCP and all applicable regulatory requirements.

Before initiating this trial, the Investigator will have written and dated approval from the Institutional Review Board for the protocol, written informed consent form, subject recruitment materials, and any other written information to be provided to subjects before any protocol related procedures are performed on any subjects.

The Investigator must comply with the applicable regulations in Title 21 of the Code of Federal Regulations (21 CFR §50, §54, and §312), GCP/ICH guidelines, and all applicable regulatory requirements. The IRB must comply with the regulations in 21 CFR §56 and applicable regulatory requirements.

13.2 Protocol Review/Changes

13.2.1 Protocol Review Committee

This study will be reviewed by the UCSF Comprehensive Cancer Center Protocol Review Committee (PRC) for scientific merit and feasibility. After initial review and approval, the study will be reviewed at least once a year for scientific merit. Any changes to the protocol are to be reviewed and approved by the PRC.

13.2.2 Institutional Review Board / Independent Ethics Committee

The study will be reviewed by the Committee on Human Research (CHR), UCSF's IRB. After initial review and approval, the study will be reviewed at least once a year as per FDA regulations (21 CFR 56.109). Any changes to the protocol and consent form are to be reviewed and approved by the CHR.

Changes are to be approved prior to being implemented, unless subject safety necessitates an immediate change, in which case approval may be given afterwards.

It is the responsibility of the Principal Investigator to keep the CHR informed of the progress of the study, including changes to the protocol or consent form, exceptions or deviations from the protocol, and any new developments which may affect subject safety or willingness to participate.

13.3 Investigational Device Exemption (IDE)

While LC Bead™ is an FDA-approved device, LC Bead™ loading with doxorubicin is not an FDA-approved application of the device. Therefore, an Investigational Device Exemption (IDE) application will be filed with the FDA.

The clinical investigation will not begin until the FDA has determined that the study under the Investigational Device Exemption (IDE) is allowed to proceed and the Investigator has received a letter from FDA stating that the study is fulfills the IDE application requirements.

13.4 Data Safety Monitoring

All subjects will be followed closely in clinic post-procedure by a medical oncologist and/or hepatologist, and interventional radiologist for signs of potential complications from the procedure. Patients will be discussed bi-weekly at the gastrointestinal oncology site committee meeting for the first month following each DEB-TACE. After the first month following the last DEB-TACE treatment, patient's progress will be monitored at 3 month intervals for a year.

The sponsor-investigator shall immediately conduct an evaluation of any unanticipated adverse device effect [21 CFR 812.46(b)].

13.5 CCC Data Safety Monitoring Committee

13.5.1 Oversight and Monitoring Plan

The UCSF-CCC Data Safety Monitoring Committee (DSMC) is responsible for monitoring data quality and patient safety for all UCSF-CCC institutional clinical studies. A summary of DSMC activities for this study includes:

- Review of subject data
- Review of suspected adverse reactions considered “serious”
- Monitoring every six months (depending on study accrual)
- Minimum of a yearly regulatory audit

13.5.2 Monitoring and Reporting Guidelines

Investigators will conduct continuous review of data and patient safety at weekly study group or site committee meetings where the results of each patient's treatment are discussed and the discussion is documented in the minutes. The discussion will include the number of patients, significant toxicities as described in the protocol, dose adjustments, and observed responses. Quarterly summaries will be submitted to the DSMC for review. All grade 3-5 AEs and SAEs will be entered in the OnCore® database.

All institutional Phase 2 or 3 studies are designated with a moderate risk assessment. The data is monitored twice per year with twenty percent of the subjects monitored (or at least three subjects if the calculated value is less than three).

13.5.3 Review and Oversight Requirements

Adverse Event Reporting

Adverse Events (AEs) will be recorded on the OnCore® database; all grade 3-5 expected and unexpected AEs will be recorded and updated at each visit.

Unanticipated/Serious Adverse Event Reporting

Unanticipated/Serious Adverse Event reporting will be in accordance with the UCSF-Committee on Human Research Regulations and Code of Federal Regulation Title 21 Volume 8 Part 812.150. See also section 14.4.

Per IDE regulations (21 CFR 812.150(a) (1) and 21 CFR 812.150(b) (1)), unanticipated adverse device effects will be reported to the FDA within 10 working days of first learning of the event.

UCSF CHR website for guidance in reporting serious adverse events

http://www.research.ucsf.edu/chr/Guide/Adverse_Events_Guidelines.pdf

If the SAE is death, and is determined to be possibly, probably or definitely related to the investigational drug or any research related procedure, the event must be reported to the DSMC Chair or his designee within 24 business hours. The reporting procedure is by personal communication via phone or in person with written documentation of the one-on-one communication via e-mail with a copy of the e-mail to DSMC Administrator and DSMC Analyst.

Review of Adverse Event Rates

All grade(s) 3-5 adverse events, whether or not unexpected, and whether or not considered to be associated with the use of DEB-TACE, will be entered into OnCore®, UCSF's Clinical Trial Management System.

All grade(s) 3-5 adverse events entered into OnCore® will be reviewed on a monthly basis at the Site Committee meetings. The Site Committee will review and discuss the selected toxicity, the toxicity grade, and the attribution of relationship of the adverse event to the procedure. All grade(s) 3-5 adverse events will be followed-up until SAE has been resolved.

In addition, all suspected adverse reactions considered “serious” entered into OnCore®, will be reviewed and monitored by the Data and Safety Monitoring Committee on an ongoing basis and discussed at DSMC meetings, which take place every six weeks.

If a death occurs during the treatment phase of the study or within 30 days after the last procedure and it is determined to be related either to DEB-TACE or to a study procedure, the Investigator or his/her designee must notify the DSMC Chair within 1 business day of knowledge of this event. The contact may be by phone or e-mail. All patient deaths (anticipated or unanticipated) will also be reported to the FDA as they occur.

Increase in Adverse Event Rates

If an increase in the frequency of Grade 3 or 4 adverse events (above the rate reported in the Investigator Brochure or package insert) is noted in the study, a report should be submitted to the DSMC at the time the increased rate is identified. The report will indicate if the incidence of adverse events observed in the study is above the range stated in the Investigator Brochure or package insert.

If at any time the Investigator stops enrollment or stops the study due to safety issues, the DSMC Chair and DSMC Manager must be notified within 1 business day via e-mail. The DSMC must receive a formal letter within 10 business days and the CHR must be notified.

Study Progress – Quarterly Review

Principal Investigators are required to submit quarterly study progress reports regarding the trial to the DSMC. These reports must include an update on accrual, information about any new amendments or updated consents and a summary of grade 3 and 4 toxicities (expected and unexpected) and all internal SAE reports. At the time of the quarterly report, all external DSMB reports and/or external formal audit reports that were received during the reporting quarter are to be sent to the committee.

These quarterly reports are reviewed at Data Safety Monitoring Committee meetings. These reports are required: February 1, May 1, August 1, and October 1. Failure to submit such reports may result in trial suspension.

Data Safety Monitoring Committee Contacts:

DSMC Chair: [name]
[contact]
Email: [contact]
Address: [name]
UCSF
[name]

DSMC Monitors
[name]
UCSF Helen Diller Family
Comprehensive Cancer Center
[name]

